## **E. Setting and Participating Institutions**

The study will be conducted with healthcare institutions that already utilize Radimetrics software, and that contribute data to the UCSF Radiation Dose Registry (UCSF-RDR, see F below). Purchase of Radimetrics demonstrates our collaborators' commitment to assessing and optimizing CT doses, and facilitates the standardized collection of radiation dose data across diverse institutions. Any healthcare institution that uses Radimetrics, and is able to electronically transfer data to the UCSF-RDR using this software (some institutional firewalls preclude doing this), is eligible for inclusion in the study. All Radimetrics customers were invited to participate in the project through an email invitation that was sent broadly to each customer. All customers interested in participating and who could complete the logistical requirements (establish data connections, complete data use agreements, complete institutional review board approvals, create a local quality improvement team and agree to complete the study aims) were invited to participate in the trial.

The healthcare institutions included below are participating in the study. Some of the institutions listed below include a single physical facility, whereas others have many associated facilities. While we encouraged all facilities associated within each healthcare institution that contribute a minimum number of examinations (120 scans within a three month period) to participate, a healthcare institution could participate even if only some of its facilities wanted or were qualified to participate. The included institutions provide geographic, socioeconomic, age, and racial/ethnic diversity of patients; contain representation from the major manufacturers and types of equipment used and diversity in delivery models. Healthcare institutions outside the U.S. are included, as CT efforts around dose optimization have been going on for far longer in Europe, and doses may be different from those in the U.S. The institutions noted with an asterisk are located outside the U.S.

	Institution	Abbreviation	Number of Facilities
(*)	University Hospital of Basel	BAS	2
	Center for Diagnostic Imaging	CDI	41
	Community Health Network	CHN	8
	Children’s Mercy Hospitals and Clinics	CMH	2
	City of Hope	COH	1
	Einstein Medical Center	EMC	4
(*)	University of Duisburg-Essen	ESN	4
	East Texas Medical Center	ETMC	9
	Emory Health System	EU	11

## **F. UCSF Radiation Dose Registry**

A secure central CT radiation dose registry, the UCSF Radiation Dose Registry (UCSF-RDR), has been created at UCSF to pool data across the collaborating institutions and facilities. This registry was funded by a separate research contract from the Patient Centered Outcomes Research Institute (PCORI). Each institution or facility pools data from consecutive CT scans performed at their institution or facility on their local server, and these data are transferred and pooled at UCSF. All facilities that contribute to the registry currently use Radimetrics - a web-based, medical imaging, radiation dose-monitoring software product owned by Bayer that quantifies the radiation delivered in CT scans. Radimetrics links to medical image archiving and communication systems to collect examination information and CT dose data delivered. Data come from the output of individual scanners using DICOM (Digital Imaging and Communications in Medicine) headers and structured reports on scanners when available, or optical character recognition if necessary. Data are collected for each radiating event (series). Monte Carlo simulation estimates absorbed and effective doses. The software also collects the image for calculating size-specific doses. These details allow valid, nuanced, and readily understandable metrics to be assembled for radiation dose within each facility.

The radiation data stored within the CT examination file (stored in DICOM data) are pooled directly from the machines where the CT scans are performed, or from the PACS (Picture Archiving and Communication Systems) where the scans are reviewed and stored on the local Radimetrics instance. The data are stripped of identifiers and in real time are then submitted to the UCSF-RDR. All identifying information, other than study date and time, is stripped or obfuscated, prior to submission to the registry. The data now stored in the registry allow us to access facility-specific radiation dose data on all consecutive CT examinations conducted at each of the collaborating facilities.

## **G. Institutional and Facility Surveys**

Several surveys will be administered to each facility to understand the organizational factors that may influence their dependence on other facilities within

their overall umbrella healthcare institution and thus how they will be randomized in the trial, and to assess institutional factors and facility factors that might influence dose indices and implementation of dose optimization following audits.

We will administer two types of surveys to capture facility-level characteristics:

1) structural and organizational aspects of each facility's CT imaging work flow (organizational survey)

2) cultural and behavioral aspects of each facility's approach to CT imaging, especially as regards patient safety, quality improvement, power and decision-making, etc. (implementation survey)

We administered the organizational survey prior to randomizing facilities. This survey collected information on structural and organizational patterns at our various facilities, including their size and type, numbers of personnel of different types (e.g. CT technologists, physicists, radiologists, residents, administrators, etc.), number of CT scanners, number of CT imaging protocols, how often protocols are reviewed, and who has the authority to change them. The organizational survey includes a combination of quantitative and qualitative questions.

We will administer our implementation (or "cultural") survey four times over the course of the study. This survey will collect information on imaging and operational practice patterns that could affect dose levels and abilities or willingness to change doses. The implementation survey includes a series of likert-scale questions that ask respondents for their opinions about practice patterns at their facility. Collectively we anticipate that trends across a number of conceptual "domains" could have correlational and predictive power related to CT dose.

We will use the surveys to understand and measure facility-level characteristics as they pertain to CT imaging. The second primary purpose of the surveys is to assess how facility-level characteristics correlate with CT dose levels at baseline. For example, are their systematic relationships between the number of CT imaging protocols at a facility and their CT dose levels.

The third primary purpose of the surveys is to assess how facility-level characteristics predict changes in CT dose levels throughout our study. For example, we might hypothesize that facilities with a strong "culture" of continuous quality improvement or CT protocol reassessment could experience greater reductions in CT dose in response to the interventional components of our study.

### **G.1 Organizational Survey**

We are including 116 individual facilities in the project. While several individual facilities might be owned or run by a single umbrella organization (healthcare institution), they all could function similarly (collectively) or differently (independently), or two could function jointly and a third separately.

The primary unit of comparison will be the individual facility. The primary unit for randomization will be the facility cluster, referring to a group of facilities within a healthcare institution that have a high degree of integration so that separate randomization would not be possible without contamination. We identified 84 facility clusters.

#### Determining facility clustering:

Highly integrated facilities within a single institution (e.g. with technologists, radiologists, and physicists moving freely between facilities/hospitals and sharing process for CT) will be considered a single facility "cluster" for the purpose of determining our randomization units. On the other hand, independently functioning facilities within a single system will be treated as separate facility clusters for the purpose of randomization.

We determined the independence of the facilities using an organizational survey and a derived CT facility independence index. The organizational survey highlights important features at each healthcare institution that we anticipate could influence how radiation doses relate to CT practices. We surveyed parent institutions and their component facilities, asking questions designed to gauge how much they functioned independently from their parent system, and

whether they should be considered clustered with other facilities for the purpose randomization.

Organizational survey questions that we used to derive the CT facility independence index focused on the processes used to develop CT protocols, sharing radiology personnel, sharing best practices, and requiring external approval on protocols. Using a 7-point scale (scored from 0 to 6 points), facilities with a higher score were deemed to be more independent than facilities with a lower score. Facilities that scored 3 points or higher were considered independent (i.e. little sharing of process or staff, with significant internal decision making on protocols). When facilities were considered "dependent" (scoring lower than 3 points), they were grouped with the other facilities in their parent institution with which they identified the sharing of staff and practices, forming a facility cluster.

Facilities will be randomized in the trial by facility cluster (the group of facilities considered dependent on another). However, the primary unit of comparison to assess the impact of the interventions will be the individual facility. When reports are provided to each facility, they will be shown the doses at their own facility, their own doses in comparison to all other facilities that are part of their umbrella institution, and in comparison to other all other facilities in the trial.

## **G.2 Institutional and Facility Implementation Surveys and Interviews**

Since we are implementing the strategies in highly diverse environments, we will study institutional and facility factors associated with doses at baseline and change in dose after the different interventions. The goal is to understand the hospital environments and cultures that are conducive to adopting strategies to improve doses. We will assess the relationship between hospital characteristics (such as readiness for change, and hierarchical arrangement of how CT protocol decisions are made) and the likelihood of the interventions succeeding to lower and optimize doses.

Surveys and interviews will be conducted at each facility because decision-making, organizational culture, and details of how CT protocols are set can differ between facilities even if they share staff and processes. For example, we will survey facility and radiology leaders to understand personal priority for optimizing CT radiation doses, perceived value of audit reports, perceived barriers to improvement, and relevant quality improvement strategies in development or implementation. We will ask the radiology administrative leader about training of personnel performing CT scans and proportion done outside normal workdays. We will ask about their reasons for purchasing Radimetrics, its use thus far, whether it has met expectations, and its impact on CT practice. We also will ask questions about the culture of quality improvement. The survey will include questions from the CPCQ, PPC-RS.

When assessing the relationship between survey results and success/failure of implementation, each facility will be considered separately.

We will ask collaborators to engage organizational leaders at their facilities, including at a minimum a non-radiology health system leader, chief radiologist, lead CT technologist, radiation safety expert, and departmental administrator. Leaders will participate in surveys and ultimately help implement systems-based strategies (such as locking CT protocols).

We will use an adapted PPC-RS from the National Committee for Quality Assurance that focuses on practice system infrastructure. This will include assessment of factors involved in dose management (e.g., systematic review of individual case dosages, department policies to standardize dosage, radiologist and technologist agreements to follow policies, processes to address staff who do not achieve dosage improvements, staff and patient education about radiation risks, etc.). The follow up surveys will try to include, at minimum, a radiologist and technologist from each facility.

### **G.3. Administration of the Surveys**

Upon agreement to participate in the study, each healthcare facility was sent a link to complete an organization survey, and a request to provide a graphical depiction of

their organizational structure. Each facility within the institution was asked to complete a questionnaire to provide further context about their relationship with the larger parent institution and other facilities within their institution. The questionnaire focus on staff composition, protocol development and maintenance, making changes to protocols, level of practice sharing, and commitment to dose optimization. Upon completion, questionnaires were returned to study coordinators, who reviewed and followed up with facilities whenever further information or clarification was necessary.

Once the study begins, we will email invitations to complete a REDCap (Research Electronic Data Capture) survey in year 1, prior to the beginning of the RCT. The survey invitation will be sent to an authority in the radiology department: the site lead champion, radiologists and technologists at baseline. REDCap surveys will again be sent to each hospital periodically (after the simple audit and prior to the multicomponent intervention, and 4-6 months and then 12 months after the multicomponent intervention) to inquire whether the recommended CT improvements were implemented and/or remain in place. The radiologists and technologists will be invited to participate in our REDCap survey. We will offer incentives, in the form of raffle drawings for prizes, to those who complete the survey within the given time periods.

## **H. Study Population and Unit of Analysis**

CT doses will be measured at the examination (i.e., encounter) level. Because examinations from the same machine, facility, and institution are structurally nested (hence non-independent), we will use appropriate statistical techniques to account for this correlational structure.

### **H.1 Included Patients and CT Examinations**

We will include consecutive patients who undergo a diagnostic CT at a participating facility from November 2015 to December 2018. We will include CT scans of the head, chest, and

abdomen and pelvis. As an exploratory analysis, we will also evaluate combined chest/abdomen/pelvis (CAP) exams.

## **H.2 Excluded Patients and CT Examinations**

- Patients over the age of 99 years will be excluded.
- Musculoskeletal (i.e., spine and extremity) CT scans will be excluded because the methodology for assessing their doses is less developed, and organ doses and cancer risk are lower for these examinations.
- CT scans of combined areas (other than combined chest/abdomen/pelvis) will be excluded because of the complexity of estimating dose.
- CT scans conducted at external institutions and sent to the Picture Archiving and Communication System (PACS) systems of the participating facilities will be excluded because these do not reflect CT practices at participating facilities.
- CT scans performed to guide radiation therapy will be excluded
- CT combined with Positron Emission Tomography (PET-CT) scans will be excluded.
- CT scans used to guide procedures and biopsies will be excluded.

## **H.3 CT Examination / CT Encounter as the primary unit of dose assessment**

Data will be assembled from the UCSF-RDR for patient level variables and CT examination (more clearly conceptualized as an encounter) level variables. An encounter is a complete CT study, which can include imaging of more than one anatomic area and can also include several irradiating events (such as a scan with intravenous contrast and a scan without intravenous contrast). The unit of CT dose assessment will be the examination (encounter) and include all irradiating events that occurred as part of the examination. If a patient undergoes two or more scans as part of that examination (encounter) – for example a scan with contrast and a scan without contrast – the dose metrics will be combined and summed for that examination (encounter).

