### **J.3 CT Dose Metrics**

The radiation dose data will be assembled and stored for each radiation event. Radimetrics extracts direct measures of dose for each radiating event from the CT reports (CTDIvol and DLP) and calculates effective dose. Radiation dose indices will include effective dose, CTDIvol, and DLP. Our primary outcome measure will be effective dose. CTDIvol and DLP will be analyzed as secondary outcomes.

Assessing diagnostic accuracy is outside the scope of this project. However, we will ask radiologists on surveys about their satisfaction with image quality as part of the pre- and post-intervention interviews and surveys and will assess the association between satisfaction and dose.

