## **L.2. Multicomponent Intervention**

The multicomponent intervention will, in addition to the audit reports, provide a more detailed, tailored, facility-specific feedback (more detailed audit report) that will match the information provided on the audits to workable interventions and actionable suggestions for lowering doses. For example, not only will high dose protocols be identified, but also facilities will be provided with guidance on technical parameters that they could alter to match the performance of the best performing facilities. Further, the multicomponent intervention will include an invitation to participate in quality improvement collaborative calls where facilities will meet via teleconference regularly (weekly over 8 weeks) to learn about quality improvement and share experiences and challenges with adopting the various practices that we are promoting. These regular meetings between a UCSF established Change Team and a hospital created Implementation Team will help guide the implementation of the key aspects of the intervention.

Facilities will receive recommendations targeted to performance, which will be sent to individuals, identified by the PI at each facility, but will ideally include facility leads, heads of radiology departments, and Implementation Team leaders. Recommendations will focus on specific, alterable, technical factors (e.g., scan length); specific protocols to use more or less frequently (e.g. multiphase protocols); protocol modifications based on cross-facility analyses, etc. Recommendations will be tailored to the facilities practices. The audit reports will be a starting point for discussions about strategies and techniques to improve CT dose levels.

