## **N. Statistical Analysis**

### **N.1 Quantitative Analyses**

For each trial phase, we will compare radiation doses from a baseline period before that intervention starts with doses in a post intervention period, separated by a “washout” period during which facilities should have adequate time to a) absorb the feedback and messages from the intervention, and b) implement changes in scanning practices if and how they so choose.

The pre-audit/intervention and post-audit/intervention periods will vary in length of time according to: a) which type of intervention (simple or multicomponent), and b) which track (randomization group) the facilities are in. Please see Section M for details.

The primary outcome measure will be effective dose. Secondary outcomes will be CTDIvol and DLP. For each anatomic area studied and each dose metric, we will compare the mean dose and the percentage of CT examinations with dose levels above the baseline 75th percentile benchmark threshold. Dose metrics may be transformed (e.g., by applying the natural logarithm) prior to modeling the mean dose if necessary to meet linear model assumptions.

We will model mean doses (possibly transformed) using hierarchical linear regression and will model the percentage of doses above the threshold using hierarchical logistic regression, controlling for underlying time trends and for facility-level and patient-level covariates that could influence dose (e.g., facility size, patient age or sex, etc.). We will include random effects for machine, facility, and facility cluster to account for correlation among scans performed on the same machine, within the same facility, and/or within the same cluster of facilities. We will evaluate the effect of audit vs. no feedback on CT dose by testing whether dose levels decrease in the follow-up period after the audit vs. during the baseline period prior to the audit. We will use a similar approach for the multicomponent intervention but will include all periods in the

model, comparing post intervention to both original (pre-simple audit/intervention) baseline and new (pre-multicomponent audit/intervention) baseline after completion of the final collaborative calls of the multicomponent audit/intervention. We will use a similar approach for assessing delayed and/or longer-term changes by analyzing doses 12-15 months following the multicomponent intervention in comparison to doses in the earlier periods.

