### **CT examination-level variables (each examination/encounter may include 1 or more radiating events/ imaging acquisitions)**

Time of examination (date, day of the week, time of the day)

Machine (make, model)

Study description

Protocol name

Scan region(s):

Dose parameters of each imaging acquisition

Average mAs

Average kVp

Scan length

Pitch

Collimation

Scan thickness

CTDIvol for each imaging acquisition

DLP for each imaging acquisition

Effective Dose for each imaging acquisition

CTDIvol (average, weighted by scan length) for each examination

DLP (sum) for each examination

Effective Dose (sum) for each examination

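### Examination-level CTDIvol, a secondary outcome, is a sum under Section H.3 but a scan-length-weighted average under Appendix R.2, and the plan does not say which governs

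*Combined protocol and SAP*

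**What the plan says.** Section H.3 makes the examination (encounter) the unit of dose assessment. Where it includes more than one scan, for example with and without contrast, "the dose metrics will be combined and summed for that examination (encounter".

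Section J.3, headed CT Dose Metrics, states which metrics these are: "Radiation dose indices will include effective dose, CTDIvol, and DLP". It adds that "CTDIvol and DLP will be analyzed as secondary outcomes". Section K also calls CTDIvol a dose metric.

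Appendix R.2 gives a separate examination-level rule for each metric:
- "CTDIvol (average, weighted by scan length) for each examination"
- "DLP (sum) for each examination"
- "Effective Dose (sum) for each examination"

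Section N.1 then applies the same analysis to every metric: "For each anatomic area studied and each dose metric, we will compare the mean dose", together with the share of examinations above the baseline 75th-percentile benchmark. Section K repeats CTDIvol in the delayed-effects analysis, and Section L.1 uses every dose metric in the audit reports. None of these sections says how CTDIvol is aggregated.

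Section L.2 includes, among the recommendations facilities may receive, "specific protocols to use more or less frequently (e.g. multiphase protocols".

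**The concern.** H.3 and R.2 agree for effective dose and DLP and disagree for CTDIvol. An analyst following H.3 adds CTDIvol over irradiating events. An analyst following R.2 averages it. For an examination with one event the results are identical, so the disagreement lies entirely in multi-event examinations.

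This is more than a labelling matter because the frequency of multi-event examinations can itself change under the intervention. If some facilities respond by using fewer multiphase protocols, the two rules will record that response differently. The CTDIvol benchmark, the share above it, the estimated effect on the mean and the figures fed back to facilities all depend on the rule. Leaving the rule open also allows it to be chosen after the results are known.

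**Working it through.** The plan gives no figure that depends on CTDIvol aggregation, so there is none to reproduce. The power statement in Section O does not use it.

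**Definitions.** For an examination with events i, CTDIvol c_i and scan length L_i:
- H.3 rule: S = Σ c_i
- R.2 rule: A = Σ(c_i × L_i) / Σ L_i

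**Inputs.** The two rules come from H.3 and R.2. The documents give no CTDIvol or scan length per phase and no multiphase share, so every number below is an assumption chosen to show the behaviour of the rules.

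**One examination, two phases reduced to one, the remaining phase unchanged.**

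| Case | S before → after | A before → after |
|---|---|---|
| Equal phases, 10 + 10 → 10, equal lengths | 20 → 10 (-50%) | 10 → 10 (0%) |
| 8 + 12, lower dropped, equal lengths | 20 → 12 (-40%) | 10 → 12 (+20%) |
| 8 + 12, higher dropped, equal lengths | 20 → 8 (-60%) | 10 → 8 (-20%) |
| 8 (length 25) + 12 (length 45), lower dropped | 20 → 12 (-40%) | (200 + 540)/70 = 10.57 → 12 (+13.5%) |

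The pattern is general. Removing a phase always lowers S. It raises A if the removed phase lies below A, leaves A unchanged if it equals A, and lowers A if it lies above.

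**Check on single-phase examinations.** A 20% cut in output, 10 → 8, gives -20% under both rules.

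**Facility mean.** Let a share m of examinations have a second phase of equal length, with CTDIvol r times that of the main phase c. Then:
- mean S = c(1 + m·r)
- mean A = c[1 - m(1 - r)/2]

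Let m fall from 40% to 10%. In units of c:

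| r | mean S | mean A |
|---|---|---|
| 0.6 | 1.24 → 1.06 (-14.5%) | 0.92 → 0.98 (+6.5%) |
| 0.8 | 1.32 → 1.08 (-18.2%) | 0.96 → 0.99 (+3.1%) |
| 1.0 | 1.40 → 1.10 (-21.4%) | 1.00 → 1.00 (0.0%) |
| 1.2 | 1.48 → 1.12 (-24.3%) | 1.04 → 1.01 (-2.9%) |

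A milder change, 20% of examinations going from two equal phases to one, moves mean S from 0.8 × 1 + 0.2 × 2 = 1.2 to 1.0 (-16.7%) and leaves mean A where it was.

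**Share above the baseline 75th percentile.** This was simulated with the same fall in m, main-phase CTDIvol log-normal with SD of the log 0.4 (assumed), and 1,000,000 examinations per period. Each share starts at 25%.

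| r | Follow-up share, S | Follow-up share, A |
|---|---|---|
| 0.6 | 14.1% | 30.1% |
| 0.8 | 11.9% | 27.4% |
| 1.0 | 10.3% | 25.0% |

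**The case against.** The best defence is that the specific governs the general. R.2 is the only place that sets aggregation metric by metric, and it separates CTDIvol from the two summed metrics, which looks deliberate. The H.3 sentence is mainly there to say that every irradiating event counts. On that reading R.2 is the intended definition and H.3 is loose drafting. This is plausible, and it is why the fix below adopts R.2. It does not close the point: the H.3 sentence expressly sums, J.3 and K count CTDIvol among the dose metrics, R.2 is a variable list, and no section gives it precedence.

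The scope is also limited, and that stands. Effective dose and DLP are sums in both places, and balancing at randomization uses DLP. Multiphase use is one example among several levers in L.2, beside scan length and other protocol changes, so it does not define the intervention.

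Three stronger readings are tempting and are not supported:
- A reader might infer that the two rules give opposite answers as a matter of course. They do so only when the dropped phase lies below the examination's weighted average. With equal phases the contrast is a fall against no change, and when the higher phase goes both measures fall.
- A reader might infer that summed CTDIvol would be little more than a count of phases. It also responds to output per phase, and how far phase number dominates depends on a multiphase share that the documents do not give.
- A reader might infer that an averaged CTDIvol would hide phase reduction from the trial. That insensitivity belongs to the metric. Phase reduction still shows in DLP and effective dose, both summed and both analysed.

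**Conclusion.** The inconsistency is real and in the current text: two definitions of one secondary outcome, with no statement of which governs. It affects the CTDIvol mean, the share above benchmark, the delayed-effects analysis and the audit reports. It does not touch the primary outcome, DLP or the sample-size statement.

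That the rules differ only for multi-event examinations, and the condition for opposite signs, are arithmetic. The sizes are illustrative. For a multiphase share falling from 40% to 10% and a second phase at 0.6 to 1.2 times the first, mean summed CTDIvol falls 14.5% to 24.3%, while the averaged version moves between +6.5% and -2.9%. Actual differences depend on the multiphase mix and on how many facilities act on that recommendation. The point should be corrected before the CTDIvol analyses, but it does not threaten the trial's main conclusion.

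**What to change.** Reconcile H.3 with R.2:
- In H.3, limit the summing rule to DLP and effective dose.
- State there, and in J.3 or N.1, that examination-level CTDIvol is the scan-length-weighted average already defined in R.2.
- Use that one definition for the CTDIvol benchmark, the mean and above-benchmark analyses, the delayed-effects analysis and the audit reports.

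Reporting the number of irradiating events per examination, or summed CTDIvol, beside it is optional.

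The cost is about one sentence in H.3 and a cross-reference. Dose data are stored for each radiation event, and R.2 lists CTDIvol and scan length by acquisition, so no new data are needed. Any benchmark or audit table already built on summed CTDIvol would have to be recalculated.
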